#### 8.8.1 Urine Albumin-Creatinine Ratio and Urine Protein-Creatinine Ratio

A urine sample for urine albumin-creatinine ratio and urine protein-creatinine ratio will be collected at visits specified in the Schedule of Procedures (Appendix A). Samples should be collected while the participant is fasting (a minimum of 8 hours).

#### 8.8.2 Aldosterone and hsCRP

A plasma sample for aldosterone and hsCRP will be collected at visits specified in the Schedule of Procedures (Appendix A). Samples should be collected while the participant is fasting (a minimum of 8 hours).

#### 8.8.3 Efficacy Endpoint Laboratory Assessments

Although laboratory values that are part of the efficacy endpoints will not be provided to the sites, the Investigator will be notified of critical high LDL-C values as follows:

- If **before Day 84**, when the LDL-C values of a participant are >200 mg/dL (>5.2 mmol/L) **AND** exhibit a >50% increase compared to Baseline; or
- If after Day 84, when the LDL-C values of a participant are >200 mg/dL (>5.2 mmol/L) OR exhibit a >50% increase compared to Baseline.

These critical high values will need to be confirmed by a repeat measurement (new fasting blood sample). The Investigator should be encouraged to consult with the Medical Monitor. Investigators and the blinded study team will be informed that random sham alerts will also be sent to sites, in order to maintain the study blind.

#### 8.8.4 Managing Abnormal and Critical Laboratory Values

Any laboratory test result abnormality that fulfills the criteria for an SAE will be reported as such on the appropriate AE and SAE eCRF. Any treatment-emergent abnormal laboratory result that is clinically significant, ie, meets 1 or more of the following criteria, will be recorded as a single diagnosis on the AE eCRF:

- Is accompanied by clinical symptoms;
- Leads to a change in study drug (eg, study drug interruption or permanent discontinuation); and/or
- Requires a change in concomitant therapy or a medical intervention (eg, the addition of, interruption of, or discontinuation of, or any other change in a concomitant medication, therapy, or treatment).

These criteria apply to any protocol and non-protocol-specified safety and/or efficacy laboratory results from tests performed after the first dose of study drug that meet clinical significance criteria. These criteria do not apply to any abnormal laboratory test results which fall outside the laboratory reference range, but which do not meet clinical significance criteria (these will be analyzed and reported as laboratory abnormalities) or those which are a result of an AE or an endpoint which has already been reported.

The Investigator is responsible for reviewing laboratory test results and determining whether an abnormal value in an individual participant represents a clinically significant change from the participant's Baseline values. In general, laboratory abnormalities without clinical significance should not be recorded as AEs. Where applicable, the clinical sequelae, not the laboratory abnormality, should be recorded as the AE.

Critical laboratory values are values that may warrant medical intervention to avoid possible harm to a participant. Critical laboratory values will be defined in the Laboratory Manual for the study, and the Medical Monitor and Investigator will be notified of the occurrence of a critical laboratory value (critical high or critical low) by a special annotation (flag) in the laboratory reports provided to the sites.

If LDL-C values are confirmed critically high (see Section 8.8.3), OR if TG levels exceed 500 mg/dL (5.7 mmol/L), the Investigator may need to take appropriate medical action, which could include the following: reinforce/intensify therapeutic lifestyle changes (including diet and physical activity), increase the dose of the present statin therapy, add ezetimibe, or prescribe a more potent lipid-modifying therapy to lower LDL-C. The Investigator should use the best clinical judgment for each participant.

#### 8.9 Vital Signs

Vital signs (consisting of heart rate and blood pressure) will be measured in triplicate prior to study drug administration at applicable visits (see Appendix A). On Day 1 (Visit 2), blood pressure will be measured prior to Randomization. When available, an automated blood pressure device is recommended for collection of blood pressure and the result should be recorded to the nearest mmHg.

Vital signs will be measured using the following standardized procedures:

- Participants should not exercise, smoke, or consume caffeinated beverages or food 30 minutes prior to assessment of vital signs; and
- Vital signs should be obtained prior to ECG recordings.

## 8.9.1 Blood Pressure Monitoring

Blood pressure specifically will be measured using the following standardized procedures:

- Participants should be seated for at least 5 minutes in the examination room with the back supported, feet flat on the floor, and the measurement arm supported so that the midpoint of the manometer cuff is at heart level;
- An appropriately sized cuff should be used with the bladder centered over the brachial artery;
- The cuff size and arm used for the measurement should be recorded; the same arm should be used for all readings;
- Three seated blood pressure measurements (each measurement 1 to 2 minutes apart) should be obtained using the same arm at each site visit. Mean seated blood pressure is defined as the average of 3 seated blood pressure measurements at a single site visit; and
- If the lowest and highest blood pressure measurements are >15 mmHg apart, additional readings should be performed.

Blood pressure readings, both systolic and diastolic, will be evaluated over time by the independent DSMB, who will monitor unblinded safety data during the study on a bi-annual basis (ie, approximately every 6 months). Changes in blood pressure, as well as heart rate, will be compared between treatment groups with respect to mean and median values over time using both actual values and absolute changes from Baseline. In addition, treatment groups will be compared with respect to the incidence of hypertensive status and other vital sign abnormalities as defined in the SAP.

#### 8.9.1.1 24-hour ABPM

Participants from selected study sites who consent to participate in the ABPM substudy will have a 24-hour ABPM assessment conducted at applicable visits (see Appendix A). The 24-hour ABPM assessment at Screening (Visit 1) should be completed after the participant's eligibility has been confirmed at that visit. It should be ensured that sufficient time is allotted during Screening (Visit 1) to allow for a repeat 24-hour ABPM assessment, if the first is not successful, prior to Randomization (Visit 2). For the 24-hour ABPM assessment at Visit 6 (Day 270), it should be ensured that a repeat assessment (if necessary) is completed within the respective visit window and that the assessment is not done concurrently with other study procedures.

Please refer to the separate study manual for additional details surrounding the 24-hour ABPM assessment for the substudy.

## 8.10 Electrocardiograms

A single 12-lead ECG will be performed in the supine position after 10 minutes of rest at visits specified in Appendix A. ECGs are to be assessed for clinical significance by a qualified medical designee at the study site.

## 8.11 Physical Examinations

Physical examinations will be completed at visits specified in Appendix A. The physical examination should comprise a focused examination, which includes general, respiratory, CV, abdominal, and extremities evaluations; ophthalmological examination; and recording of weight and height. Height will be measured at Screening (Visit 1) only and used to calculate body mass index.

#### 9 STATISTICS

## 9.1 Analysis Populations

The Intent-to-Treat (ITT) Population will include all participants who are randomized into the study. Treatment classification will be based on the randomized treatment.

The Full Analysis Set (FAS) will include all participants who are randomized into the study, take any study drug, and have at least 1 post-treatment lipid data assessment. Treatment classification will be based on the randomized treatment.

The Modified ITT (mITT) Population will include all randomized participants who receive at least 1 dose of any study drug and have data for both the Day 1 and Day 84 LDL-C assessments. Treatment classification will be based on the randomized treatment.

The Per-Protocol (PP) Population will include all participants in the mITT Population who did not experience a major protocol deviation that potentially impacted the primary efficacy endpoint. The PP Population, along with the reason for exclusion, will be finalized prior to study unblinding.

The Safety Population will include all participants who receive at least 1 dose of any study drug. Treatment classification will be based on the actual treatment received. The Safety Population will be the primary population used for the safety analyses.

#### 9.2 Statistical Methods

An SAP will be finalized before database lock. Any changes to the methods described in the SAP will be described and justified as needed in the final Clinical Study Report. All study-collected data will be summarized by treatment group using descriptive statistics, graphs, and/or raw data listings. Descriptive statistics for continuous variables will include number of participants, mean, standard deviation, median, minimum, and maximum values. Analyses of categorical variables will include frequency and percentage.

Unless otherwise stated, Baseline values will be the last non-missing measurements taken prior to the participant receiving study drug.

## 9.2.1 Analysis of Efficacy

## 9.2.1.1 Primary efficacy analysis

The ITT Population will be the primary population for the efficacy analysis. Efficacy will also be analyzed using the FAS, mITT Population, and PP Population as supplementary analyses.

The primary efficacy endpoint is the percent change from Baseline to Day 84 in LDL-C in the obicetrapib group compared to the placebo group. The primary endpoint will be analyzed using an analysis of covariance (ANCOVA) model with a fixed effect for the treatment group and covariates of Baseline LDL-C, CV risk (HeFH or non-HeFH), and Baseline statin therapy (HIS or non-HIS). The least squares (LS) mean, standard errors, and 2-sided 95% confidence intervals for each treatment group and for the mean difference compared to placebo will be obtained. The model will be fit assuming unequal variances for each treatment group.

The primary estimand will correspond to a treatment policy estimand. The target population will comprise participants who are randomized into the study. The primary summary measure to assess the treatment effect will be the LS mean difference for the primary endpoint between obicetrapib

and placebo based on the ANCOVA methodology. The primary estimand will be addressed using the in-study observation period (ie, including data collected post-treatment discontinuation or post-prohibited medication use).

Missing data will be imputed for the primary efficacy analysis based on a pattern mixture model that uses a multiple imputation technique analyzed with ANCOVA with pre-specified fixed factors and covariates. If appropriate, based on the number of retrieved dropouts, missing measurements of non-retrieved dropouts will be modeled by known measurements from retrieved dropouts (ie, participants who remain in the study after treatment discontinuation) in the same treatment group. The imputation model will be further clarified in the SAP.

Additional sensitivity analyses may be carried out under secondary estimands and/or various assumptions for missing data. Full details will be provided in the SAP.

## 9.2.1.2 Secondary and exploratory efficacy analysis

In order to control the Type I error rate, a fixed sequential testing procedure will be implemented. In a hierarchical step-down manner, the primary endpoint will be tested first, followed by the secondary efficacy endpoints in a pre-specified order. The pre-specified order of the hypothesis testing for the secondary endpoints will be described in the SAP. No adjustment for multiple comparisons will be made for the exploratory efficacy endpoints.

Continuous secondary efficacy endpoints will be analyzed using similar methods as in the primary efficacy analysis.

Exploratory efficacy endpoints corresponding to continuous variables will be analyzed using a similar ANCOVA model as in the primary efficacy analysis. The 2-sided 95% confidence interval for LS means will be provided for continuous variables. Odds ratio and 95% confidence interval for the odds ratio will be provided for exploratory efficacy endpoints corresponding to binary variables. For time-to-event endpoints, the log-rank test, stratified by CV risk (HeFH or non-HeFH) and Baseline statin therapy (HIS or non-HIS), will be used to compare differences in the time-to-event between obicetrapib and placebo. The hazard ratio and the associated 95% confidence interval will be estimated using a stratified Cox proportional hazards model with treatment as an explanatory variable, stratified by CV risk (HeFH or non-HeFH) and Baseline statin therapy (HIS or non-HIS). Additionally, Kaplan-Meier estimates of the time-to-event will be determined and displayed graphically. The proportional hazard assumption will be evaluated, such as through the examination of complementary log-log (event times) versus log (time) plots, etc. If the proportional hazard assumption raises concerns, additional analyses will be considered and will be further detailed in the SAP. Nominal p-values will be provided when applicable. Descriptive and graphical summaries by treatment group will also be presented. A population PK analysis will be described in a separate document.

Full details of the models and analyses to be performed will be provided in the SAP.

#### 9.2.2 Analysis of Safety

The Safety Population will be the primary population for the safety analysis. All safety endpoints will be summarized descriptively.

AEs will be categorized by primary system organ class and preferred term as coded using the Medical Dictionary for Regulatory Activities category designations. Summaries of AEs, including the number and percentage of participants who experience an AE, will be provided.

Laboratory values will be summarized descriptively, including the change from Baseline, by treatment group, and overall. In addition, shift tables will be presented to describe the change in laboratory parameter values at post-Baseline visits using normal range categories (low, normal, and high).

## 9.2.2.1 Analysis of ESIs

Liver-associated enzymes and total bilirubin will be summarized by the value and change from Baseline in the value, by treatment group and visit. In addition, the number and percent of participants with abnormal values for ALT, AST, and total bilirubin will be summarized. These summaries of participants with abnormal values will be performed overall; by normal Baseline; and by abnormal Baseline for ALT, AST, and total bilirubin individually. Hy's Law criteria (>3 × ULN for either ALT or AST, with accompanying total bilirubin >2 × ULN) will also be applied to the data. Any potential Hy's Law cases will be listed separately.

Muscle-related abnormalities will be summarized by treatment group and by Baseline eGFR category.

CK levels will be summarized by the value and change from Baseline in value, by treatment group and visit. In addition, the number and percent of participants with abnormal CK values will be summarized. These summaries of participants with abnormal CK values will be performed overall, by normal Baseline CK, and by abnormal Baseline CK. Values of CK from Baseline to EOT will be summarized by treatment group and by Baseline eGFR category.

Cases of NODM will be recorded and summarized using the appropriate system organ class. These events will be summarized by severity and relationship to study drug for each treatment group. Fasting plasma glucose and HbA1c will be monitored as specified in Appendix A.

Baseline eGFR will be summarized by treatment group for actual value and for Baseline eGFR categories. Shift tables of eGFR category from Baseline to EOT will be provided by treatment group. Shift tables of urine albumin-creatinine ratio and urine protein-creatinine ratio from Baseline to EOT will be provided by treatment group.

The number and percentage of participants receiving antihypertensive medication(s) treatment at Baseline with changes to antihypertensive medication(s) due to changes in blood pressure will be summarized by treatment group.

Cases of macular degeneration will be recorded and summarized using the appropriate system organ class. These events will be summarized by severity and relationship to study drug for each treatment group.

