All participants who permanently discontinue study drug should continue scheduled study visits. If the participant declines continued onsite visits but is agreeable to telephone calls, he/she will be contacted by the Investigator periodically to assess occurrence of CV events until death, documented withdrawal of participant informed consent (in writing if allowed by local regulations), or the final closure of the study.

The Investigator should show due diligence and explore all possible options to reach a participant who fails to return for a visit. In the case of participants lost to follow-up, attempts to contact the participant must be made and documented in the participant's medical records and in source documents. Per routine, in order to avoid participants lost to follow-up, the Investigator should ask the participant at the study start for the contact details of a relative or friend who can be contacted for participant contact information in case the participant cannot be reached.

Participants should not be withdrawn from follow-up unless they explicitly withdraw consent to be contacted. All efforts should therefore be made to minimize the number of participants who withdraw consent as, in general, no further information on CV events and survival status may be collected after that point. Participants who do not want regular in-person follow-up after cessation of study drug should be offered alternative methods of follow-up, including periodic telephone follow-up, contact at study closure, or assessment of health status via treating physicians or medical records. Such participants would then not be viewed as withdrawal of consent. The Investigator must explain to the participant all options for continued participation, and document which options were refused by the participant and the reason for refusal. Withdrawal of consent to all follow-up must be ascertained and documented in writing by the Investigator, who must inform the Sponsor and document the withdrawal of consent in the eCRF and medical records.

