For participants who permanently discontinue from study treatment and who decline continued study participation, an Early Termination (ET) Visit will be scheduled as soon as possible followed by an onsite EOS Visit 35 days later. The ET Visit procedures are identical to the End of Treatment (EOT) Visit procedures. If the discontinuation occurs at a specific onsite visit, this visit will become the ET Visit and EOT Visit procedures should be followed. Participants who

withdraw consent to all follow-up will be asked about the reason(s) and will be assessed for the presence of any AEs.

For participants who completely withdraw consent, life status will be obtained at study end through public record information according to local guidelines and as allowed by local regulations.

If premature withdrawal from the study occurs for any reason, the Investigator must determine the primary reason for a participant's premature withdrawal from the study and record this information in the medical records and on the eCRF.

Withdrawn participants will not be replaced.

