## 8.2.5.4 Guidelines for monitoring and management of significant changes in renal function

If at any time after Randomization (Visit 2) a participant experiences ANY of the following, the participant will undergo a repeat confirmatory assessment as soon as is reasonably possible, preferably within 3 to 7 days of the laboratory result becoming available:

- A >25% decrease in eGFR from Baseline, calculated using the Chronic Kidney Disease Epidemiology Collaboration equation;
- An eGFR <30 mL/min/1.73 m^2, calculated using the Chronic Kidney Disease Epidemiology Collaboration equation; and/or
- An increase in serum creatinine of  $\geq 0.3$  mg/dL ( $\geq 26.5$  µmol/L) from Baseline.

In consultation with the Medical Monitor and/or nephrologist, if no alternative etiology is determined, the study drug should be discontinued if participants experience an unexplained, confirmed increase in serum creatinine of  $\geq 0.3$  mg/dL ( $\geq 26.5$  µmol/L) from Baseline or an unexplained, confirmed  $\geq 25\%$  decrease in eGFR from Baseline.

If any of these individual laboratory parameters are confirmed, such events of decline in renal function should be recorded as an ESI.

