3.1.2 Analysis Visits

Scheduled visits will be assigned to analysis visits as recorded on the CRF.

For each analysis visit, if a scheduled visit occurs within the analysis day window, then the measurement from this scheduled visit will be used. If no scheduled visit occurs or laboratory results of the scheduled visit were unreportable, the unscheduled measurement closest to the target day will be used. If measurements are equidistant to the target day, the later measurement will be used. Otherwise, unscheduled visits will not be re-assigned and will remain labelled as unscheduled. If laboratory measurements for the scheduled visit were taken while a participant was not in a fasting state and laboratory measurements are available from an unscheduled visit

during which the participant was in a fasting state (and the visit occurred within seven days of the scheduled visit), those fasted labs will be utilized in place of the unfasted labs.

Early termination (ET) visits will be assigned to analysis visits according to the visit windows in Table 2 and Table 3.

Table 2 Analysis Visit Windows (excluding Japan)

Analysis Visit	Target Analysis Day	Low Analysis Day	High Analysis Day
Day 1 (Visit 2)	1	NA	NA
Day 30 (Visit 3)	30	2	57
Day 84 (Visit 4)	84	58	132
Day 180 (Visit 5)	180	133	225
Day 270 (Visit 6)	270	226	317
Day 365 (EOT/Visit 7)	365	318	N/A

Table 3 Analysis Visit Windows (Japan Only)

Analysis Visit	Target Analysis Day	Low Analysis Day	High Analysis Day
Day 1 (Visit 2)	1	NA	NA
Day 14 (Visit 3)	14	2	22
Day 30 (Visit 4)	30	23	57
Day 84 (Visit 5)	84	58	132
Day 180 (Visit 6)	180	133	225
Day 270 (Visit 7)	270	226	317
Day 365 (EOT/Visit 8)	365	318	N/A

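### The eGFR, UACR and UPCR shift tables read participants only at EOT, so they can miss renal worsening that occurred on drug in those who stopped drug or left early

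*Protocol*

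**What the plan says.** Protocol 9.2.2.1 and SAP 3.5.2 plan a Baseline summary of eGFR and then two sets of endpoint tables: "Shift tables of eGFR category from Baseline to EOT will be provided by treatment group" and "Shift tables of urine albumin-creatinine ratio and urine protein-creatinine ratio from Baseline to EOT will be provided by treatment group".

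Three other provisions decide whose value reaches those tables.

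- **Stopping drug.** Protocol 8.2.5.4 provides, after consultation, that "if no alternative etiology is determined, the study drug should be discontinued if participants experience an unexplained, confirmed increase in serum creatinine" of at least 0.3 mg/dL, or an equivalent confirmed eGFR fall.
- **Follow-up after stopping.** Protocol 4.3: "All participants who permanently discontinue study drug should continue scheduled study visits". Only a further group gets an ET visit: "For participants who permanently discontinue from study treatment and who decline continued study participation, an Early Termination (ET) Visit will be scheduled".
- **Visit assignment.** SAP 3.1.2: "Early termination (ET) visits will be assigned to analysis visits according to the visit windows in Table 2 and Table 3". In Table 2 the last row, "Day 365 (EOT/Visit 7"), starts at Day 318; the Japan table uses the same lower limit.

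SAP 3.1.8 adds that safety data are used as available, without imputation, so a missing EOT value stays missing.

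**The concern.** Renal decline is one of the plan's events of special interest, and the protocol may withdraw drug because of it. A table read only at Day 365 then measures some of the affected participants after exposure has ended and omits others who have left. If the effect is reversible, the worsening cells of the table lose people who did worsen while exposed.

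The urine ratios are the sharper case. They are scheduled only at Visit 2 and at the V7/EOT/ET column, so a leaver's ET sample is the sole scheduled post-Baseline value. Protocol 4.3 turns an onsite visit at which such a participant discontinues into the ET visit, so that sample may lie close to the last dose. It is the most informative urine sample such a participant has, and the shift table as windowed does not use it.

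**Working it through.** The plan states no figure for this point, so there is none to reproduce. The check sets the provisions side by side and then illustrates the size.

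**1. Values available and values used.** eGFR is in the full chemistry panel (Visits 2, 5, 7) and the limited panel (Visits 1, 3, 4, 6), per Protocol Appendices A and B. Scheduled post-Baseline values: Days 30, 84, 180, 270 and 365, that is 5. The category shift table uses 1 of the 5. UACR and UPCR have 1 scheduled post-Baseline value, at V7/EOT/ET.

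**2. Where an ET visit goes.** ET visits on Days 2 to 317 map to Day 30, 84, 180 or 270 (also Day 14 in Japan). Days mapped away from EOT: 317 − 2 + 1 = 316. Days from Day 2 to Day 365: 365 − 2 + 1 = 364. Share: 316/364 = 87%. This is a share of calendar days, not of participants. The V7/EOT/ET column label might suggest that an ET value counts as EOT, but the SAP windows indicate that it does not before Day 318.

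**3. What each participant contributes to the Baseline-to-EOT tables.**

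| Course after renal decline | eGFR table | UACR/UPCR table |
|---|---|---|
| Stays on drug to Day 365 | on-drug value | on-drug value |
| Drug stopped, visits continue | off-drug value; earlier on-drug values unused | off-drug value; no earlier scheduled sample |
| Drug stopped, leaves before Day 318 with ET visit | no EOT value; earlier values unused | no EOT value; ET sample unused |

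**4. Illustration of size.** All rates here are assumptions. Take about 1600 and 800 participants (2400 at 2:1) and any-time decline of 8% and 4%, an excess of 4.0 points. Let s be the share of affected participants stopped, w the share of those stopped who leave without an EOT value, and r the share of those stopped and remaining who recover, equal in both arms. With E affected of n:

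EOT proportion = [E − E·s·w − E·s·(1 − w)·r] / (n − E·s·w), with E = 1600 × 0.08 = 128 and 800 × 0.04 = 32.

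- r = 0, w = 0 (no recovery, nobody leaves): 128/1600 − 32/800 = 8.0% − 4.0% = 4.0 points. No dilution.
- s = 0.5, r = 0.5, w = 0: 96/1600 − 24/800 = 6.0% − 3.0% = 3.0 points.
- s = 0.5, r = 1, w = 0: 64/1600 − 16/800 = 4.0% − 2.0% = 2.0 points.
- s = 0.9, r = 1, w = 0: 12.8/1600 − 3.2/800 = 0.8% − 0.4% = 0.4 points.
- s = 0.9, r = 0, w = 0.2: 104.96/1576.96 − 26.24/794.24 = 6.66% − 3.30% = 3.35 points (from unrounded values).

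With any-time decline of 6% and 4%, the excess of 2.0 points runs down to 0.2 points over the same range. Because stopping and recovery are set equal in both arms, the ratio stays near its any-time value; what shrinks is the absolute excess and the number of visible cases. A count over all post-Baseline visits would keep the full any-time difference.

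**The case against.** The strongest reply is that these tables are only part of the renal safety analysis.

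SAP 3.5.2 counts and lists, by treatment group, every eGFR fall above 25%, every eGFR below 30 and every creatinine rise of at least 0.3 mg/dL, at whatever visit it occurs. Those criteria nearly coincide with the laboratory triggers for stopping drug, so almost everyone stopped under that rule is counted, whether or not they later recover or leave. (Protocol 8.2.5.4 uses more than 25% to trigger a repeat test but at least 25% in the stopping sentence; the two should be reconciled.) TEAEs leading to discontinuation are tabulated, the DSMB reviews these events unblinded about every 6 months, and laboratory values and changes are summarized. Baseline to EOT also answers a fair question of its own, namely whether decline persists.

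This reply stands against two stronger readings that a reader might infer.

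- **That affected participants are not counted at all, so renal harm is hidden.** The any-time event counts and listing rule this out.
- **That the stopping rule empties the worsening cells.** The rule is conditional on confirmation, on no other cause being found and on consultation, and an eGFR below 30 alone is not in the stopping sentence. Category worsening is also a different event: with the SAP 3.3.4 cuts at 30, 45, 60 and 90, a fall from 62 to 58 changes category but is only 4/62 = 6.5%. That participant does not meet the eGFR stopping criterion and still shows at EOT, as does anyone who stays with irreversible decline.

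The reply does not cover everything. The renal event pools three thresholds, does not show movement between categories and excludes UACR and UPCR. The general laboratory shift tables use low, normal and high ranges, and SAP 3.5.3 limits them to parameters it does not name. An early ET urine sample may appear in a general summary under another visit, but it is not in the planned shift table. Protocol 9.2.2.1 itself lists no renal event count; only the SAP supplies one.

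**Conclusion.** The point holds for the shift tables, not for renal safety as a whole, and it is minor. The tables read one of five scheduled post-Baseline eGFR values, take an off-drug value from participants who stopped and stayed, and take none from those who left before Day 318. For UACR and UPCR they omit the only scheduled post-Baseline sample that an early leaver has.

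Understatement requires that decline reverses off drug or that affected participants leave; with neither there is none. The documents give no rates of renal decline, stopping, recovery or departure, so the size cannot be derived. The range in the illustration, from no dilution to about 90% of the absolute excess, follows entirely from assumed rates and from treating both arms alike. It supports saying that the tables can understate on-drug worsening, not that they will.

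**What to change.** Change SAP 3.5.2 only, before unblinding, and list the addition in SAP Section 6.

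1. Add a shift table from Baseline to the worst on-treatment eGFR category, by treatment group, beside the Baseline-to-EOT table. The sponsor should pre-specify the on-treatment window; neither document gives one for this purpose. The last-dose date already defined in SAP 3.3.7 can anchor it.
2. Add a missing-at-EOT column to the Baseline-to-EOT tables, and state what EOT means for them.
3. For UACR and UPCR, use the V7 or ET sample, whichever the participant has, whatever analysis window it falls in. Show samples taken off drug separately.
4. Refer from these tables to the any-time renal event counts, so that they are read together.

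**Cost.** Programming only; the values are already scheduled for collection, and no clinical rule changes. The worst-value table carries more measurement noise. That noise may be unequal between arms if time on drug or triggered repeat tests differ, so the table should use scheduled visits only or be shown with and without unscheduled repeats. One gap remains: a participant who stops drug early and stays has no scheduled on-drug urine sample after Baseline, so the table can label that value as off drug but cannot replace it.
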